11.0 Efficacy Measures

Collection of efficacy data to support product approval is not part of this feasibility study. As such, no formal statistical hypothesis is being posed and/or applied. As part of this feasibility study, the following data will be collected and evaluated:

- Monosyllabic word recognition performance in quiet using the CNC word test pre-to
 post device activation at 12 months will be compared, tabulated and summarized.
 Specifically, the CNC word scores postoperatively will be compared to the pre-implant
 word score for the implanted ear. Individual and group comparisons will be completed.
 The intent is to understand the benefit of the implant treatment option and restoration
 of auditory input results in improved speech understanding.
- 2. Audiometric hearing thresholds at the 12 month postoperative test interval will be compared to preimplant thresholds. Individual and group comparison is confirmatory to assess that hearing acuity in the non-implanted ear (better hearing ear) is not affected significantly by cochlear implant treatment in the opposite ear (poorer hearing ear).
- 3. Sentence recognition scores in noise using the AzBio Sentence Test pre-to-post device activation will be compared, tabulated and summarized. Specifically, the everyday, bilateral listening condition AzBio sentence scores at the 12 month postimplant test interval will be compared to the preimplant bilateral sentence score. Individual and group comparisons will be conducted. The intent of this comparison is to evaluate the contribution and/or benefit of the implant treatment option (provision of binaural sensory input) in an asymmetrical hearing loss population.
- 4. To understand if the restoration of binaural sensory input in a single-sided deafness/asymmetrical hearing loss population results in improved ability in lateralization of sound. Using the AzBio Sentence metric, the month postimplant outcome will be compared to preoperative ability. Individual and group comparisons will be conducted.
- 5. The Speech, Spatial Qualities (SSQ) questionnaire score comparison pre-to-post device activation will be conducted to provide a subjective measure of patient perceived hearing performance/auditory benefit with this combined technology. The SSQ will aid in providing a measure of subjective perceived benefit in the restoration of binaural auditory input. SSQ scores at 12 months postimplant will be compared to the preimplant scores. Individual and group comparisons will be conducted.
- 6. Additional subjective outcome scales may also be assessed and evaluated to understand if restoration of binaural auditory input results in improvement of quality of life. This will include the Tinnitus Handicap Inventory and Sponsor developed subjective scales.

The results of the efficacy measures are expected to be generalizable to the Medicare beneficiary population. It has been shown that elderly patients can benefit from cochlear

implantation and age is not considered a limitation for cochlear implant surgery (Otol Neurotol. 2016 Jan;37(1):46-51. Outcomes After Cochlear Implantation in the Very Elderly. Wong DJ1, Moran M, O'Leary SJ.). The findings of several studies suggest that cochlear implantation can be equally effective in improving speech recognition in older patients as compared to younger adults (Schwab, B., Gandolfi, M., Lai, E., Reilly, E., Singer, L. and Kim, A.H. (2015) The Impact of Age on Cochlear Implant Performance. International Journal of Otolaryngology and Head & Neck Surgery, 4, 329-337., Zwolan, T.A., Henion, K., Segel, P., Runge, C. (2014). The role of age on cochlear implant performance, use, and health utility: a multicenter clinical trial. Otol Neurotol. 35(9):1560-8; Otol Neurotol. 2017 Jan;38(1):54-59. Cochlear Implantation in the Elderly: Does Age Matter? Rohloff K1, Koopmann M, Wei D, Rudack C, Savvas E.; Rev Laryngol Otol Rhinol (Bord). 2013;134(3):119-24. Cochlear implantation in older patients: outcomes and comparisons. Rafferty A, Tapper L, Strachan D, Raine C.)

Efficacy results will be published on clinicaltrials.gov within one (1) year of the completion date of the study.

12.0 Safety Measures

The collection of safety data to support product approval is not part of this study. For these objectives, safety is referred to as freedom from procedure and/or device-related adverse events. No formal statistical hypothesis will be sought.

Safety results will be published on clinicaltrials.gov within one (1) year of the completion date of the study.

12.1 Adverse Event Reporting and Assessment

An adverse event (AE) is defined as any undesirable clinical occurrence experienced by a study subject when using the HiResolution System or when undergoing research procedures, whether or not the AE is considered to be device-related. The definition of an AE also includes any event related to any study procedures or to any underlying medical condition present at baseline that increases in severity during the study. An underlying medical condition that was present at the time of enrollment will not be reported as an AE, but any increase in severity during the study will be reported as an AE.

All device-related and non-device-related adverse events (AEs) will be tracked and reported accordingly throughout the feasibility study as defined above in the investigational plan and in accordance with requirements of an IDE investigation. The AEs will be recorded and tracked between completion of the informed consent form (signed and dated) and two weeks after the participant's last study visit. The number and percent of all subjects experiencing adverse events will be summarized by type and frequency of event. Adverse Events will be recorded and will include but are not limited to the following information [refer to Appendix A for Case Report Forms (CRFs)]:

The following risks associated with surgery and/or cochlear implantation are identified as anticipated Adverse Events:

- General risks
 - General anesthesia
 - Postoperative pain
 - Bleeding or infection
 - Possibility of damage to the facial nerve
 - Balance related issues (i.e. dizziness, vertigo)
 - Numbness
 - Swelling or discomfort around the ear
 - Taste disturbance
 - Increased ringing in the ears (tinnitus)
 - Neck pain
 - Skin reaction
 - Leakage of inner ear fluid or cerebrospinal fluid which may increase the risk of meningitis. Meningitis is an infection in the fluid and tissue that surround the brain and spinal cord. There are two types viral and bacterial meningitis; bacterial being the most serious type and has been reported in cochlear implant recipients. The Centers for Disease Control (CDC) recommends for patients pursuing cochlear implantation to be up to date on age-appropriate pneumococcal vaccination. More information about the CDC recommendations can be found at http://www.cdc.gov or by calling [name]. It is recommended to discuss vaccinations and surgical risks with the subjects prior to the scheduled procedure.
 - Hearing may sound different when the cochlear implant is turned on
 - Insertion of a cochlear implant electrode will likely result in the loss of any residual hearing in the implanted ear.
- Risks associated with implantation of the internal cochlear implant device and electrode array
 - The presence of a foreign body (implant) may result in irritation
 - Redness or breakdown of the skin in the area around the implant receiver/stimulator and/or rejection of the device
 - The electrode array may migrate partially resulting in reduced hearing ability
 - Misplacement of the electrode array may result in non-auditory sensations which may require additional medical treatment, surgery and/or removal of the device, however, this is considered a rare circumstance
 - Electrical stimulation may increase tinnitus, facial nerve stimulation, balance related issues (i.e. dizziness, vertigo) or pain
 - Implantation in the cochlear may preclude the use of future implant technology

- Device failure of operation that may perhaps require removal of the device
- A risk of additional loss natural hearing as a factor of chronological age (i.e. presbycusis) and/or etiology of the hearing loss may be experienced
- Any study participant experiencing a shift in audiometric threshold of 30 dB or greater pure tone average threshold shift across 250-1000 Hz from baseline to post-operative visits will be reported as an anticipated Adverse Event under this feasibility study.
- Risks specifically associated with the clinical population evaluated in this feasibility study, that of single-sided deafness/asymmetrical hearing loss
 - It is possible that the electrical stimulation of the cochlear implant when provided to a poorer hearing ear that has not heard for some period of time may take a period of adjustment and may subjectively be a competing signal and potentially create binaural interference. Speech perception ability in noise and sound localization ability may be impacted. Should this binaural interference occur to a level in which speech understanding is affected, the participant will have the option to remove the external cochlear implant sound processor. This removal may be dependent on the listening environment or in specific listening conditions. If the latter event occurs, and the participant chooses removal of the cochlear implant sound processor, he/she will be counseled by the managing hearing care specialist as to the alternative, conventional options and/or a return to an untreated state. These risks and mitigations are further provided below in Section 13.1 of the Investigational Plan.

The following definitions will be used to classify AEs.

A *serious adverse event* (SAE) is an event that: a) led to a death, or b) led to a serious deterioration in the health of the subject that:

- resulted in a life-threatening illness or injury,
- resulted in a permanent impairment of a body structure or of a body function,
- required inpatient hospitalization or prolongation of existing hospitalization,
- resulted in medical or surgical intervention to prevent permanent impairment to body structure or a body function, or
- led to fetal distress, fetal death or a congenital abnormality or birth defect.

An adverse device effect (ADE) is any untoward and unintended response to a medical device. A serious adverse device effect (SADE) is an event related to the device that resulted in any of the consequences characteristic of a serious adverse event (SAE) or that might have led to any of the consequences if suitable action had not been taken or interventions had not been made or if circumstances had been less opportune.

An unanticipated adverse device effect (UADE) is any serious adverse effect on health or safety; any life threatening problem or death caused by, or associated with, a device, if that effect, problem, or death was not previously identified in nature, severity, or degree of incidence in the investigational plan or application; or any other unanticipated serious problem associated with a device that relates to the rights, safety, or welfare of subjects.

All adverse events and adverse device effects, serious and non-serious, will be recorded on the Adverse Event Report Case Report Form [CRF] (see Appendix A for all CRFs). Information to be recorded on the CRF should include, but is not limited to:

- Date of onset of the adverse event
- Date reported to the Sponsor
- Description of the event, duration and severity
- Seriousness
- Treatment/Intervention course of action taken
- Outcome/Status (resolved, improving, no change, worsening). In case of an SAE, the subject must be followed until the serious adverse device effect is resolved or no reasonable improvement is expected.

Evaluation of any SAE, SADE, or UADE will be conducted promptly. All AEs related to the HiResolution system that impact device safety in the first three months after device implantation will be adjudicated by a Medical Monitor. Confirmed UADEs will be reported to the FDA according to 21 CFR Part 812.150(b) (1) within 10 days after receiving event, to participating Investigators and to IRBs according to their requirements. If it is determined that an event or effect presents an unreasonable risk to subjects, this study, or those parts of the study presenting that risk, will be terminated no later than 5 working days after the determination is made and no later than 15 working days after Advanced Bionics/Clinical Research first received notice of the event.

[figure not shown]

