Using AzBio Sentence Test in Quiet - One list presented at 40 dBA in soundfield in the
participant's bilateral, everyday listening condition. The participant is asked to identify if
the sentence was detected from the left or right speaker. The sentence delivery from
right or left speaker is randomized.

Note: Participants may or may not be aided in one or both ears thus, testing may be aided or unaided or a combination during test administration). The test setup is as follows:

• Participant will be centered and faced forward between a right and left speaker (each positioned in corners of the audiometric suite at 45° respectively)

Self-Assessment Questionnaire(s):

- Speech, Spatial and Sound Qualities (SSQ) Questionnaire standard version (Version 5.6)
- Tinnitus Handicap Inventory (THI) Administered only if participant has reported tinnitus
- Sponsor developed patient report questionnaire/scale

Implant Surgery:

Conducted at participant's managing hearing care clinical center. Note: Implant surgery to be completed within 26 weeks of the Baseline Visit. If the surgery date exceeds this time frame, Baseline measures including audiometric and speech perception testing will need to be reevaluated.

Initial Device Activation/Fitting:

Device activation should occur within 3 to 6 weeks postimplant surgery.

Device Programming – Sound Processor Fitting: Specific Instruction:

 Study participants are to be provided with a standard everyday program with the following FDA approved signal processing strategy(ies):

HiRes™ Optima with ClearVoice

Additional programs and parameter settings are deferred to the guidance and recommendations of the participant's managing hearing care specialist.

Audiometric Testing:

- Unaided air-conduction thresholds using insert earphones at 250, 500, 1000, 2000, 4000 and 8000 Hz; unilateral, each ear. Clinical masking as appropriate.
- Unaided bone-conduction hearing thresholds at 500, 1000, 2000 and 4000 Hz;
 unilateral, each ear

Adverse Event Assessment:

An adverse event assessment is completed by the investigator at each test interval. An assessment will be completed additionally if an adverse event has occurred outside of the scheduled study test intervals (i.e. unscheduled visit).

3 and 6 Month Postimplant Test Intervals:

The three and six month post-device activation visits to occur within 12 and 24 weeks respectively (+/- 14 days) of the participant's device activation date.

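### The Section 12.1 adverse event definition is narrower than the protocol's own recording window and scope, and leaves some periods to the undefined word *using*

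*Combined protocol and SAP*

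**What the plan says.** Section 12.1 builds the definition in two parts. The first is an exposure condition: an AE is "any undesirable clinical occurrence experienced by a study subject when using the HiResolution System or when undergoing research procedures". For events that meet this condition, a link to the device is not required; they count "whether or not the AE is considered to be device-related". The second part widens the definition: "The definition of an AE also includes any event related to any study procedures or to any underlying medical condition present at baseline", provided that the condition gets worse during the study. A condition already present at enrolment is not itself reported, but "any increase in severity during the study will be reported as an AE".

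The next paragraph sets scope and time. On scope: "All device-related and non-device-related adverse events (AEs) will be tracked and reported accordingly throughout the feasibility study as defined above". On time: "The AEs will be recorded and tracked between completion of the informed consent form (signed and dated) and two weeks", the latter counted from the last study visit. The planned summary is the number and percent of subjects with AEs, by type and frequency.

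Three other places bear on when the system is in use. Section 9.0 says "Device activation should occur within 3 to 6 weeks postimplant surgery" and allows up to 26 weeks from the Baseline Visit to surgery before baseline measures must be repeated. Section 12.1 says that if binaural interference affects speech understanding, "the participant will have the option to remove the external cochlear implant sound processor". The Glossary (Section 3.0) counts the internal implant, the external processor and the fitting software all as parts of the system. No section says what it means to be *using* it.

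**The concern.** A window that opens at consent, with a scope that names non-device-related events, leads the reader to expect that events are recorded first and attributed afterwards. The definition does not deliver this. Its first part depends on what the subject was doing when the event happened. The clause that waives device-relatedness helps only events that already meet that condition. Outside it, a new event that is not a worsening baseline condition has to be linked to a study procedure before it is an AE at all. Because the scope sentence refers back to the definition, it carries the same limit.

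Two things are at stake. The first is consistency: two sites reading the same words could record the same event differently, and the only planned safety summary is a count and percentage in a very small group. The second is the order of decisions. Section 12.0 equates safety with the absence of events attributable to the procedure or the device. That classification is most reliable when made on recorded events. An event set aside as unrelated at the outset cannot be reclassified later. Section 7.1 states that the study is unblinded, so attribution is made by people who know the treatment.

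**Working it through.** The plan gives no figure on this point to reproduce. The check sets the definition against the window, period by period.

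**Inputs.** Definition, scope and window: Section 12.1. Baseline to surgery, up to 26 weeks, and surgery to activation, 3 to 6 weeks: Section 9.0. Components of the system: Section 3.0. Sample size: up to 15 (Sections 2.0 and 10.0) or up to 20 (Section 7.3).

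**Rule as written.** An occurrence is an AE if at least one of these holds: (a) it happens while the subject is using the system; (b) it happens during a research procedure; (c) it is related to a study procedure; (d) it is a baseline condition that has worsened. Section 12.1 separately makes a pure tone average shift of 30 dB or more across 250–1000 Hz, from baseline to a postoperative visit, a reportable AE.

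**Test case.** Take a new clinical event, not a worsening of a baseline condition, not a threshold shift, outside any research procedure, and thought unrelated to study procedures. Then (b), (c) and (d) are all false and only (a) can make it an AE.

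| Period | Window open? | (a) using the system? | AE as written? |
|---|---|---|---|
| Consent to implantation (surgery up to 26 weeks from baseline) | Yes | No, on any reading | No |
| Surgery to activation (3 to 6 weeks) | Yes | Undefined: implant in place, processor not yet fitted | Depends on the reader |
| After activation, processor on | Yes | Yes | Yes |
| After activation, processor off | Yes | Undefined: implant in place, processor not worn | Depends on the reader |

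The first row is a gap on the literal text. The second and fourth are ambiguities.

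**Does other text close the gap?** Section 9.0 first lists an AE assessment at device activation; none is listed under the Baseline Visit or Implant Surgery. The extra assessment between scheduled visits is triggered when an AE has occurred, so it relies on the same definition. The seriousness categories in Section 12.1 are used to classify AEs, so an event not regarded as an AE may not reach them. None of these supplies a wider rule.

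**Scale of one discrepancy.** One subject counted differently moves the percentage of subjects with an AE by 1/15 = 6.7 percentage points, or by 1/20 = 5.0 points. This is the weight of a single subject. It does not estimate how often such a discrepancy would occur.

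**The case against.** The strongest reply is that nothing here conflicts. The protocol promises to record AEs as it has defined them, and a time window and a narrower definition can both be followed. That stands: a reader might infer that the definition contradicts a promise to record every event from consent, but no such promise is made.

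Second, a reader might infer that outside device use an event counts only if it is judged related. That is too strong. A worsening baseline condition counts without a relatedness judgement, and so does a threshold shift of 30 dB or more. Events during research procedures count whether or not they are device-related.

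Third, the period after surgery is not expressly excluded. The system includes the internal implant, so an implanted subject can fairly be read as using it before activation or with the processor off. Surgery is a step in the study schedule, so events linked to it enter as procedure-related. Dizziness, bleeding and infection are listed as anticipated AEs, so it cannot be said that such events would never be recorded. All of this stands, and it makes the post-surgical problem one of ambiguity.

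Fourth, the documents describe no formal relatedness screen before recording, and the case report forms in Appendix A are not in the text available. That also stands: attribution before capture is a possible consequence of the wording, not a described procedure.

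Finally, this is a feasibility study with no hypothesis test, and unrelated events before implantation fall outside the safety concept in Section 12.0. That limits the consequence. It does not settle who decides that an event is unrelated, or when, and the all-AE count and percentage remain affected.

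**Conclusion.** The concern holds as a mismatch and an ambiguity. The definition is narrower than the window and scope stated beside it. On a literal reading, a new event before implantation and outside a research procedure is left out unless it is judged procedure-related or is a baseline condition getting worse, although recording is already open. For the 3 to 6 weeks before activation, and for time with the processor off, the answer turns on one undefined word.

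The first conclusion assumes that the definition is applied literally. The second assumes that sites could reasonably differ over *using*. Sites may in practice record more than the text requires.

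A reader might infer that AE rates are biased downward. Under-recording is a plausible direction, but the documents show neither direction nor size. A reader might also add 26 + 6 = 32 weeks before activation, set this against 26 + 6 + 50 + 2 = 84 weeks of possible recording (the 50 being the 48-week visit plus 14 days), and quote 38%. That figure should not be used. It is a maximum, 26 of its 32 weeks are waiting time before surgery, and it measures time, not missed events. The post-surgical part is at most 6/84 = 7%, and it is ambiguous, not excluded. The length of processor-off time is not given.

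**What to change.** In Section 12.1, delete the condition that the occurrence arise during use of the system or during research procedures. Define an AE as any undesirable clinical occurrence in an enrolled subject from signed consent to two weeks after the last study visit, whether or not the system is in use and whether or not the event is thought to be related. State that relation to the procedure and to the device is assigned after the event has been recorded. The scope sentence that refers back to the definition then needs no change, and *using* no longer has to be defined.

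The cost is one sentence in the protocol and slightly more non-serious, unrelated events to record in a small study.

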The twelve month post-device activation visit to occur within 48 weeks (+/-14 days) of the participant's device activation date.

Important Note: The participant is to be tested at each scheduled study test interval using the standard everyday program ().

Please confirm that this program is selected prior to testing.

Audiometric Testing:

- Unaided air-conduction thresholds using insert earphones at 250, 500, 1000, 2000, 4000 and 8000 Hz; unilateral each ear. Clinical masking as appropriate.
- Unaided bone-conduction hearing thresholds at 500, 1000, 2000, and 4000 Hz;
 each ear.

Speech Perception Testing:

• CNC Word Test in Quiet - Two lists of 50 words presented at 60 dBA in the *implanted* ear only

- AzBio Sentence Test in Noise Two lists presented in the following soundfield conditions at 60 dBA with a +5 dB SNR using speech-spectrum noise in the participant's everyday, bilateral listening condition. The following test conditions are to be conducted:
 - Speech Front, Noise Front (Target and Noise 0° azimuth)
 - Speech Front (0° azimuth), Noise directed to the implanted ear (90° or 270° azimuth)
 - Speech Front (0° azimuth), Noise directed to the non-implanted ear (90° or 270° azimuth)

Lateralization Testing:

AzBio Sentence Test in Quiet - One list presented at 40 dBA in soundfield in the
participant's bilateral, everyday listening condition. The participant is asked to identify if
the sentence was detected from the left or right speaker. The sentence delivery from
right or left speaker is randomized.

Note: Participants may or may not be aided in one or both ears thus, testing may be aided or unaided or a combination during test administration. The test setup is as follows:

• Participant will be centered and faced forward between a right and left speaker (each positioned in corners of the audiometric suite at 45° respectively)

Self-Assessment Questionnaire(s):

- Important Note: The Speech, Spatial and Sound Qualities Questionnaire standard SSQ version (5.6) is administered at this test interval.
- The Tinnitus Handicap Inventory (THI) Administered only if participant has reported tinnitus
- Glasgow Benefit Inventory
- Sponsor developed patient report questionnaire/scale

Adverse Event Assessment:

An adverse event assessment is completed by the investigator at each test interval. An assessment will be completed additionally if an adverse event has occurred outside of the scheduled study test intervals (i.e. unscheduled visit).

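### Section 11 calls the better-ear comparison confirmatory, but a descriptive analysis of 15 or 20 people can only estimate better-ear change; the related 30 dB adverse-event rule names no ear

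*Combined protocol and SAP*

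**What the plan says.** **Better-ear comparison.** The Synopsis lists contralateral-ear unaided thresholds at 12 months against preimplant as a separate endpoint. Section 11.0, item 2 plans individual and group comparisons and calls them confirmatory that the better ear is not significantly affected by implanting the other ear. Sections 10.0, 11.0 (opening) and 12.0 each state that there is no formal hypothesis. Section 10.0 plans, as a minimum, individual tabulation and counts of subjects who improve, stay the same or decline. It then gives an open-ended list of descriptive statistics: counts, means, medians, standard deviations and percentages. No confidence interval is named, and no cut-off separates no change from decline. The Synopsis and Section 10.0 give up to 15 subjects; Section 7.3 gives up to 20.

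**Hearing-shift rule.** Section 12.1 states, for any study participant, that a "30 dB or greater pure tone average threshold shift across 250-1000 Hz from baseline to post-operative visits will be reported as an anticipated" adverse event. No ear is named. Audiometry at 12 months is done at "250, 500, 1000, 2000, 4000 and 8000 Hz; unilateral each ear". Two nearby bullets differ on this. One names its ear: "Insertion of a cochlear implant electrode will likely result in the loss of any residual hearing in the implanted ear". The other does not: "A risk of additional loss natural hearing as a factor of chronological age (i.e. presbycusis) and/or etiology of the hearing loss may be experienced". The adverse-event summary is planned as follows: "The number and percent of all subjects experiencing adverse events will be summarized by type and frequency of event".

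**The concern.** Whether implanting the poorer ear leaves the better ear unharmed is a stated question of this study. To confirm that something is not affected, a plan needs a limit of acceptable change and an analysis able to exclude change beyond it. Neither is present. A report that follows the plan could present a clean descriptive table as confirmation when the data would also fit a material rate of harm.

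The unnamed ear in Section 12.1 touches the same question from the safety side. Read literally, a better-ear shift of 30 dB or more carries the same anticipated label as the implanted-ear loss that the plan regards as likely. The planned summary does not have to separate the two. The label also bears on the definition of an unanticipated adverse device effect, which depends on whether the effect "was not previously identified in nature, severity, or degree of incidence in the investigational plan or application".

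**Working it through.** **The plan's own figure.** The sample size cannot be reproduced. Section 10.0 calls up to 15 subjects sufficient but gives no alpha, power, effect, SD, margin or target precision. The check is therefore what a comparison of this size can show. I use n = 15 (Section 10.0) and n = 20 (Section 7.3). Both are ceilings, so fewer evaluable subjects would make everything below less precise.

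**1. Shift counts, exact (Clopper-Pearson) two-sided 95% interval.**

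With 0 events the upper limit is 1 − 0.025^(1/n):
- n = 15: 1 − 0.025^(1/15) = 0.218
- n = 20: 1 − 0.025^(1/20) = 0.168

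With 1 event the lower limit is 1 − 0.975^(1/n) and the upper limit is the 0.975 quantile of Beta(2, n − 1):
- n = 15: 0.17% to 31.95%
- n = 20: 0.13% to 24.87%

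**2. Chance of seeing no shift at all**, (1 − p)^n. The documents give no true rate p, so the values are assumptions shown as a range.

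| Assumed true rate | n = 15 | n = 20 |
|---|---|---|
| 5% | 46.3% | 35.8% |
| 10% | 20.6% | 12.2% |
| 15% | 8.7% | 3.9% |

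**3. Events-free sample needed to exclude a rate**, one-sided 95%: the smallest n with (1 − p)^n ≤ 0.05, that is ln 0.05 / ln(1 − p) rounded up. This is 29 subjects for a 10% rate and 59 for a 5% rate. Both exceed the planned numbers.

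**4. Mean better-ear change.** The 95% CI half-width is t(0.975, n − 1) × SD / √n:
- n = 15: 0.554 SD
- n = 20: 0.468 SD

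The documents give no SD. If it were 5, 7.5 or 10 dB (assumed), the half-width would be 2.8, 4.2 or 5.5 dB at n = 15, and 2.3, 3.5 or 4.7 dB at n = 20.

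**5. The 30 dB rule, read against its neighbours.** This part is textual. The rule's unit is the participant, while the measurement is per ear. One adjacent bullet specifies the implanted ear and another specifies none, so the list does not settle the question. Two readings remain open: implanted ear only, or either ear. Only the second overlaps with Section 11.0, item 2.

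**The case against.** **On the confirmatory wording.** The same section opens by disclaiming a hypothesis, and the Synopsis and Section 7.2.1 say that efficacy data for approval are not part of the study. The word may be loose prose for a descriptive check. Section 10.0's list is open, so an interval is not excluded. The bounds above would apply to any study of 15 people, and they concern a shift criterion that the plan has yet to state. All of this is fair. Having no hypothesis is acceptable in a feasibility study, and none is asked for here. What stands is that the sentence claims a property the analysis does not have, and that an interval which is merely not excluded is not planned.

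**On the 30 dB rule.** The list is introduced as risks of surgery and implantation, and the rule follows the heading on the internal device and electrode array. List nesting may also have been lost in the text. The implanted ear may well be meant.

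A reader might infer that the label keeps better-ear harm out of expedited reporting or out of sight. The documents do not support that:
- The definition of an unanticipated effect also turns on severity and degree of incidence, and it keeps a general clause for other unanticipated serious problems. It refers to the application as well as the plan. The application and the separate risk report cited in Section 13.1 are not available here.
- A shift that "resulted in a permanent impairment of a body structure or of a body function" could still qualify as serious.
- The case report form asks for "Description of the event, duration and severity". The form itself is not shown and may record the ear.
- Better-ear thresholds are compared individually at 12 months in any case.

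**On generalizability.** A reader might also link the point to Section 11.0's expectation that results apply to Medicare beneficiaries. That passage argues from age and makes no claim about the better ear, so it carries no weight here.

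**Conclusion.** The main point holds. As planned, the comparison can estimate better-ear change but cannot confirm its absence. Zero shifts would leave a true rate of up to 21.8% (n = 15) or 16.8% (n = 20) within the two-sided exact 95% interval. At an assumed true rate of 10%, 15 subjects would show no shift about one time in five. These figures rest on independent subjects, complete 12-month audiometry and a shift criterion fixed in advance.

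The secondary point holds only as an ambiguity. The 30 dB rule does not say which ear it covers, and its literal reading includes the ear that Section 11.0 sets out to show is unaffected. No event has been identified that would go unreported.

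This should be corrected, because it changes what the trial can say about the better ear.

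**What to change.** 1. **Section 11.0, item 2.** Remove the confirmatory wording. Report the mean better-ear change from baseline to 12 months with a 95% CI. Add the number and percent of subjects shifting, by a criterion the sponsor states in advance, with an exact 95% CI. Describe both as estimates.
2. **Section 12.1.** Reconcile the 30 dB rule with its neighbouring bullets and with Section 11.0, item 2 by stating which ear or ears the anticipated label covers. How better-ear shifts are classified is for the sponsor to decide. Tabulate hearing-shift adverse events by ear.

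**Cost.** The change is a rewording of one Section 11.0 item and one adverse-event rule, plus one table split. Thresholds are already measured in each ear at baseline, activation and 12 months, so there are no extra visits or tests. The downside is slightly more tabulation and a less favourable-sounding claim.
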